In ACTT-2, subjects receiving the combination treatment of baricitinib and remdesivir had a shorter median time-to-recovery of 7 days (95% confidence interval (CI), 6 to 8 days) when compared with patients who received remdesivir and placebo (8 days; 95% CI, 7 to 9 days) with control [rate ratio for recovery [RRR] 1.16, 95% CI 1.01 to 1.32; P=0.03]. Patients who received combination treatment were 30% more likely to have clinical improvement by day 15 than those in the control arm (odds ratio [OR] 1.3; 95%CI 1.0 to 1.6). The patients who benefited the most from combination treatment were those requiring high-flow oxygen or non-invasive ventilation at enrollment with a median of 10 days to recovery compared with 18 days in control group (RRR 1.5, 95% CI 1.1 to 2.1) and the best clinical improvement by day 15 (OR 2.2; 95% CI 1.4 to 3.6). Baricitinib also showed benefit to those on low flow oxygen with a median of 5 days to recovery compared with 6 days in control group (RRR 1.17, 95% CI 0.98 to 1.39) and the clinical improvement by day 15 (OR 1.2; 95% CI 0.9 to 1.6). Patients who received combination treatment with baricitinib and remdesivir and those in the control arm had a similar incidence of adverse and serious adverse events including infections and venous thromboembolic events (VTE).

The Randomized Evaluation of COVID-19 Therapy (RECOVERY) trial is a controlled, open-label randomized trial, involving all major hospitals in the UK. The trial compared a range of possible treatments in patients who were hospitalized with COVID-19. Included, was a treatment arm assigned to receive oral or intravenous dexamethasone (at a dose of 6 mg once daily for up to 10 days) or to received usual care alone. Overall, 22.9% in the dexamethasone group and 25.7% in the usual care group died within 28 days after randomization (age-adjusted rate ratio, 0.83; 95% confidence interval [CI], 0.75 to 0.93; P<0.001). In the dexamethasone group, the incidence of death was lower than that in the usual care group among patients receiving invasive mechanical ventilation (29.3% vs. 41.4%; rate ratio, 0.64; 95% CI, 0.51 to 0.81) and among those receiving supplemental oxygen without invasive mechanical ventilation (23.3% vs. 26.2%; rate ratio, 0.82; 95% CI, 0.72 to 0.94) but not among those who were receiving no supplemental oxygen respiratory support at randomization (17.8% vs. 14.0%; rate ratio, 1.19; 95% CI, 0.91 to 1.55). Remdesivir was not used routinely in the RECOVERY trial.

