5. SAMPLE SIZE CONSIDERATIONS

Sample Size for Primary Analysis

The primary hypothesis will be a test of the difference in proportions surviving without requiring invasive mechanical ventilation between the two treatment arms by Day 29. Estimating the expected treatment effect of baricitinib relative to dexamethasone is difficult given the differences between the ACTT-2 and RECOVERY studies as discussed above. In [Table 1](#) the first row of treatment effects is based on estimates from the ACTT-2 and RECOVERY results amongst the cohort that most closely resembles the ACTT-4 target population (those in ordinal 5 and 6). In the second row, the relative findings were changed to assume a gradual improvement in standard of care. This corresponds to a sample size of 1382 subjects. Sample size calculations were based on an exact unconditional score test of proportions using StatXact v11.1.0. Assuming 8% lost to follow-up, the sample size is planned to be approximately 1500 subjects.

The remaining lines demonstrate the power of the proposed sample size. There is good power of this trial for multiple scenarios unless the proportions surviving without invasive mechanical ventilation is much higher than anticipated (thought to be unlikely) or the difference in the proportions is smaller than anticipated (possible, but difficult to anticipate given the data available).

The protocol defined primary analyses were to be based on Kaplan-Meier estimates of the proportion of patients surviving without mechanical ventilation by Day 29 using a large sample normal approximation with Greenwood's variance formula. Accordingly, power for the final analysis is assumed to be equal or slightly higher than the power for the exact score as seen below.

Table 1: Sample Size Estimates and Study Power

Total Sample Size	Proportion Dex Arm Surviving Through Day 29 Without Mechanical Ventilation	Proportion Bari Arm Surviving Through Day 29 Without Mechanical Ventilation	Power (unconditional exact score)	Power (KM + Greenwood)
- Baricitinib from ACTT-2 (OS 5 and 6) - Dexamethasone relative efficacy (only those on oxygen) from RECOVERY applied to ACTT-2 placebo arm	1342	0.814	0.87	80.9% 80.6%
Estimate of the above proportion applied to current outcomes given gradual improvement in care	1382	0.85	0.9	80% 80.5%
Other scenarios showing study power for the sample size of 1382	1382	0.9	0.95	94.5% 94.9%
	1382	0.9	0.925	37.0% 37.5%
	1382	0.85	0.925	99.4% 99.4%
	1382	0.8	0.875	96.6% 96.6%

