6. GENERAL STATISTICAL CONSIDERATIONS

6.1. General Principles

This is a double-blind, placebo controlled randomized trial with a two-sided type I error rate of 0.05. Secondary hypotheses have been ordered according to relative importance. These will be described according to the appropriate summary statistics, e.g.:

- Percentages/proportions/odds ratios for categorical data. For tabular summaries of percentages/proportions, the denominator (e.g. number of subjects with non-missing data) will be displayed.
- Means, median, and range for continuous data, median for time-to-event data.

Confidence intervals will be generated; for the primary analysis, the confidence level will take into account the group-sequential design of the trial (see Section 6.6 and Section 8.1) whereas 95% confidence intervals will be generated for secondary and exploratory outcomes. Proportions will be estimated using the Kaplan-Meier Day 29 survival estimate with Wald-type confidence intervals assuming large-sample normality with standard errors estimated using Greenwood's formula for variance. For hazard ratio and odds ratio estimates, Wald confidence intervals will also be used. For other efficacy outcomes (e.g. proportions), Wilson or Score confidence intervals will be used. For safety outcomes, exact (e.g. Clopper-Pearson) confidence intervals will be used.

When calculating treatment effects (e.g., differences, hazard ratios, odds ratios) and when using treatment arm as a covariate in regression modeling, the baricitinib + placebo + remdesivir arm will be used as the reference group. For regression modeling that uses strata variables defined in Section 6.4, the first stratum listed for each variable in that section will be used as the reference group.

For the final comparison of Day 29 mechanical ventilation free survival, the following SAS pseudocode will be used to obtain Kaplan-Meier survival estimates, standard errors and confidence intervals, for each treatment within strata. Survival estimates and standard errors will be used to calculate the test statistic and compared to a standard normal distribution as in Section 8.1.1.

```
proc lifetest data=dataset plots=(s) method = km outsurv = survests;
  time TimeVariable * CensorVariable(1);
  strata TreatmentVariable StrataVariable;
run;
```

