For the analysis of mechanical ventilation free survival, subjects will be censored at the time of medication/therapy initiation. For the analysis of the key secondary outcome, if a subject reports use of any of the medications/therapies prior to their Day 15 assessment, then the subject's last clinical status score prior to medication/therapy use will be used as their Day 15 outcome. For the mortality analyses, subjects will be censored at the time of medication/therapy initiation. For the analysis of the proportion of subjects that do not progress to Clinical Status Ordinal Score of 6, 7, or 8 by Day 29, subjects will be censored at the time of medication / therapy initiation. For the recovery analyses, subjects will be censored at the time of medication/therapy initiation. If a subject recovered prior to use of any of the medications/therapies, then the subject will still be counted as a recovery in the sensitivity analysis.

The effect of on-study treatment on select efficacy outcomes will also be explored among subjects who reported use of HMG-CoA reductase inhibitors (statins), angiotensin receptor blockers (ARBs), or angiotensin converting enzyme inhibitors (ACEIs) via subgroup analyses.

Lastly, the effect of treatment on the primary and key secondary efficacy outcomes will be explored via regression modeling controlling for age, duration of symptoms prior to randomization, baseline d-dimer, and baseline CRP values as continuous covariates.

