8.1.2. Hierarchical Sequence of Secondary Endpoints Analyses

Analyses described in this section will be subject to the fixed-sequence hierarchical testing procedure described in Section 6.8. Any reference to p-values in this section is conditional on preceding hypothesis tests in the hierarchy.

If a superior test fails to reject the null hypothesis, the analyses will still be performed to provide estimated effects with confidence intervals for relevant statistics and associated confidence-interval by-arm, but p-values will not be generated. Confidence intervals for all analyses of secondary endpoints, will be 95% confidence intervals.

8.1.2.1. Clinical Status Ordinal Scale at Day 15

In the mITT population, the distribution of the 8-point Clinical Status ordinal score at Study Visit Day 15 (not necessarily actual study day 15), will be analyzed using a proportional odds model with treatment arm and actual baseline ordinal score (baseline ordinal score 5 or baseline ordinal score 6) as covariates. The treatment odds ratio estimated from the model will be presented along with the p-value, (Table 21). This analysis will be repeated for the As Treated population (Table 22). The Study Visit Day 15 clinical status score will be depicted graphically using shifted bar plots; the outcomes will be presented by actual baseline ordinal score and treatment group (Figure 13).

8.1.2.2. Proportion of Subjects Not Progressing to Clinical Status 6, 7, or 8 by Day 29

In the mITT population and among only those with an actual baseline ordinal score of 5, the proportion of subjects not progressing to ordinal score 6, 7, or 8 by Day 29 (see Section 3.3.4) will be analyzed using the same modeling approach as the primary outcome and described in Section 8.1.1. Kaplan-Meier curves (Figure 31) and p-values with estimates of proportions at the Day 29 study visit will be calculated and accompanied by confidence intervals (Table 23).

8.1.2.3. Mortality by Day 29

Mortality through Day 29 will be analyzed as a time to event endpoint (see Section 3.3.5). A table will present median time to event along with 95% confidence intervals overall for each treatment arm along with the hazard ratio estimate and log rank p-values. Differences in time-to-event endpoints by treatment will be summarized with Kaplan-Meier curves (Figure 27).

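### The confirmatory Day 15 proportional odds model leaves out age, which the SAP uses as a covariate only in supportive models; if age is prognostic, this gives up some power

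*SAP*

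**What the plan says.** **Day 15 (Section 8.1.2.1).** The score "will be analyzed using a proportional odds model with treatment arm and actual baseline ordinal score". Those are the only two covariates, and the PROC LOGISTIC pseudocode in Section 6.1 likewise has only treatment and the baseline stratum.

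**Mortality (Section 8.1.2.3).** "Mortality through Day 29 will be analyzed as a time to event endpoint", with log-rank p-values. The text names no stratification. The Table 70 shell says the log-rank test is stratified.

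**Recovery (Section 8.1.2.4).** A log-rank test stratified by actual baseline score.

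**Age.** Section 9.1 lists it among the baseline characteristics. Section 6.4 explores the primary and key secondary outcomes in regression models with "age, duration of symptoms prior to randomization, baseline d-dimer, and baseline CRP values as continuous covariates". The same set of covariates appears in the shells for Tables 16, 21, 24 and 29 (primary, Day 15, progression and recovery). Age group is also a subgroup factor for the primary and key secondary outcomes. Section 8.2 places its analyses outside the hierarchy. No mortality model includes age: the supplemental Cox model in Sections 8.2.4 and 9.4 has treatment, baseline score and their interaction.

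The SAP gives no reason for leaving age out of the confirmatory tests.

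**The concern.** The plan itself selects age as a covariate worth adjusting for, then keeps it out of the one confirmatory model where it could be added with a single term. In a randomized comparison, a baseline variable that predicts outcome, included in a prespecified model, raises power without touching the type I error rate. Day 15 is the second of five steps in Section 6.8, so a miss there ends formal testing of progression, mortality and recovery.

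The supportive adjusted models do not make up for this. They carry no weight in the hierarchy, and they tie age to CRP. Section 4.3 excludes CRP from sites using a high-sensitivity assay from every analysis that uses CRP, so those subjects lack the covariate. Age has no such restriction.

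**Working it through.** **1. The plan's own sample size.** Inputs from Sections 5 and 6.1: 0.85 vs 0.90, two-sided 5%, 80% power; 1:1 allocation is assumed. Per arm,

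n = [1.96·√(2·0.875·0.125) + 0.8416·√(0.85·0.15 + 0.90·0.10)]² / 0.05² = (0.9167 + 0.3925)² / 0.0025 ≈ 686,

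so 1372 in total. The plan says "This corresponds to a sample size of 1382 subjects" from an exact score test; the normal approximation at 691 per arm gives 80.3% power. Then 1382/0.92 ≈ 1502, matching "Assuming 8% lost to follow-up, the sample size is planned to be approximately 1500 subjects". These figures concern the primary comparison and do not depend on age. The SAP gives no power for the Day 15 test.

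**2. Effect of adding age to the Day 15 model.** Everything except N = 1382 is assumed: marginal treatment odds ratio about 1.32, 20% of subjects at score 6, a score log odds ratio of 1.5, control-like category probabilities of 0.30, 0.30, 0.05, 0.08, 0.08, 0.07, 0.06 and 0.06 from best to worst, and age standardized with a linear effect. There were 500 simulated trials per setting, each fitted with and without age. The gain is the squared ratio of mean Z, which approximates the ratio of effective sample sizes.

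| Age OR per SD | Estimate (SE) without age | Estimate (SE) with age | Gain ratio | Power |
|---|---|---|---|---|
| 1.0 | −0.272 (0.0974) | −0.272 (0.0974) | 1.00 | 79.4% → 80.4% |
| 1.25 | −0.284 (0.0974) | −0.286 (0.0976) | 1.01 | 82.6% → 84.0% |
| 1.5 | −0.272 (0.0974) | −0.281 (0.0979) | 1.06 | 80.2% → 82.8% |
| 2.0 | −0.272 (0.0974) | −0.299 (0.0990) | 1.17 | 80.0% → 85.4% |
| 2.5 | −0.266 (0.0974) | −0.312 (0.1000) | 1.30 | 79.4% → 86.0% |

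With 500 runs a power near 80% has a simulation standard error of √(0.8·0.2/500) ≈ 1.8 points, so the gain ratio is the better guide. The 1-point change at OR 1.0 is noise.

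**3. Cross-check by hand.** Treating the outcome as a latent logistic variable with variance π²/3 = 3.29, the gain is about 1 + b²/3.29, where b is the log odds ratio per SD:

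- OR 1.25: 0.223²/3.29 = 0.015
- OR 1.5: 0.405²/3.29 = 0.050
- OR 2.0: 0.693²/3.29 = 0.146

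That is about 1.5%, 5% and 15%, in line with the simulation. On 1382 subjects, the simulated gains of about 1%, 6% and 17% equal roughly 14, 83 and 235 subjects.

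**4. Where the gain comes from.** At OR 2.0, Z goes from 0.272/0.0974 = 2.79 to 0.299/0.0990 = 3.02. The standard error rises slightly; the estimate moves further from zero because it is now conditional on age.

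**5. Mortality and recovery.** A Cox model stratified by baseline score, with and without age, stood in for the log-rank test. Mortality (about 7.5% deaths, HR 0.6 assumed) gained 2%, 6% and 9% at age HRs of 1.5, 2.0 and 2.5 per SD. Recovery (about 93% recovering, HR 1.17 assumed) gained 3%, 10% and 22% at age HRs of 0.87, 0.77 and 0.67. Standard errors again stayed flat.

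**The case against.** The strongest reply is that nothing here is wrong. The Day 15 test is prespecified, adjusts for the clinical-status stratification factor as the primary analysis does, and keeps its error rate. Every gain above rests on assumed strengths for age, and at the modest end it is negligible. All of that stands: this is an efficiency point.

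Several stronger readings are tempting, and the documents do not support them:

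- *The plan loses precision.* It does not; the standard errors stay flat or rise slightly. The loss is in power.
- *Leaving age out has no benefit.* The stratified log-rank test needs no functional form for age and a Cox test does. That is a fair reason to keep the log-rank tests as confirmatory.
- *The mortality test adjusts for baseline score alone.* Section 8.1.2.3 names no stratification at all; only Table 70 does.
- *Missing d-dimer and CRP shrink the supportive models.* Section 6.5 gives imputation rules for these laboratory values. The loss the SAP does state is the high-sensitivity CRP exclusion, and it gives no size for it.
- *The introduction shows that age is strongly prognostic here.* The figure it cites, "age-adjusted rate ratio, 0.83; 95% confidence interval [CI], 0.75 to 0.93; P<0.001", is a treatment effect from another trial, not the strength of age on these outcomes.

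The fixed-sequence argument also has limits. Testing reaches Day 15 only if the primary rejects, and the progression step after it would remain unadjusted.

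Timing is a fair concern as well. Section 15.3 says all subjects were enrolled by version 2.0, and Section 6.2.1 records a futility analysis in April 2021. But version 2.0 itself changed the weighting of the primary test statistic, and Section 4.2.6 unblinds the sponsor and the coordinating center only after the Day 29 lock.

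**Conclusion.** The point holds as an inexpensive gain in power for the Day 15 test, not as an error. Age is available and already chosen by the SAP as a covariate, yet it is absent from the confirmatory proportional odds model. The gain is about 1%, 6% and 17% in effective sample size at assumed age odds ratios of 1.25, 1.5 and 2.0 per SD (power 80.0% to 85.4% at 2.0), and zero with no loss if age is not prognostic. These figures depend on the assumed strength and linear form of age, the assumed outcome distribution and 1:1 allocation; the SAP supplies none of them.

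For mortality and recovery, the documents do not make a case for replacing the log-rank tests. What needs correcting there is the mismatch between Section 8.1.2.3 and Table 70, and the absence of any mortality model that includes age.

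**What to change.** Before the Day 29 unblinding, staff who have seen no unblinded or futility results should make and document these changes:

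1. **Section 8.1.2.1, the Section 6.1 pseudocode and the notes to Tables 21 and 22:** add continuous age to treatment and actual baseline score, and state that the odds ratio is conditional on age.
2. **Section 8.1.2.3:** state that the log-rank test is stratified by actual baseline score, in agreement with Table 70.
3. **Mortality and recovery:** keep the stratified log-rank test as confirmatory, and add a Cox model with continuous age, stratified by actual baseline score, as a supportive estimate.

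The cost is a short amendment with a stated rationale and one extra model term. No new data are needed. The downsides are a conditional rather than marginal odds ratio and an assumed linear effect of age.

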8.1.2.4. Time to Recovery

In the mITT population, the time to recovery, as defined in Section 3.3, will be analyzed using a stratified log rank test to compare treatment to control through Day 29. Stratification is based on actual baseline Status ordinal score (ordinal score 5, ordinal score 6). As noted in Section 3.3, all deaths within 29 days will be considered censored at Day 29 with respect to time to recovery. Conceptually, a death corresponds to an

infinite time to recovery, but censoring at any time greater than or equal to Day 29 gives the same answer as censoring at Day 29; both correspond to giving deaths the worst rank.

The treatment hazard ratio estimate and confidence interval and p-value from the stratified log rank test will be presented ([Table 28](#)). The median time to event and 95% confidence intervals will be summarized by treatment group and actual baseline Clinical Status ordinal score. Kaplan-Meier curves will also be generated by treatment arm ([Figure 15](#), [Figure 16](#), [Figure 17](#)).

8.2. Additional Secondary Efficacy and Sensitivity Analyses

This section describes the planned sensitivity analyses for the Primary Efficacy analysis and for the secondary efficacy outcome measures that will be executed outside of the hierarchical testing procedure governing the study-wide type 1 error described in the preceding section. Results described here are considered supportive and corroborative to the primary analysis from Section [8.1](#).

Analyses of the key secondary outcome measure will be explored in the specified subgroups described in Section [6.4](#). Analyses of the other secondary outcome measures will be performed by treatment arm only and repeated for specified subgroups described in Section [6.4](#) and Section [6.7](#) via stratified analyses. As with the analyses described in Section [8.1.2](#), tabular summaries will follow the structure of the main tabular summaries planned for each outcome with the modification that stratified estimates will be provided in separate rows. Forest plots will display confidence intervals of outcomes/estimates across subgroups, where applicable.

All secondary efficacy analyses will be performed in the mITT population. As Treated analyses may be explored to investigate consistency of results compared to the mITT analyses.

8.2.1. Sensitivity and Corroborative Analyses of the Primary Endpoint

The primary analysis will be repeated in the As Treated analysis population and in the ITT analysis population. The tabular and graphical summaries described in the previous section will be replicated for this As Treated analysis ([Figure 5](#)) and by baseline ordinal score ([Figure 6](#) and [Figure 7](#)).

Sensitivity analyses will be performed using Cox proportional hazards models to estimate the hazard ratio or progression to mechanical-ventilation or death ([Table 16](#)). A Cox model will be fit with binary indicators for treatment group and actual baseline Clinical Status ordinal score (5 or 6) as well as a treatment * actual baseline Clinical Status score interaction terms. The models will be fit to the mITT analysis population. The treatment group hazard ratios and CIs will be reported for both sets of models and the interaction term p-value will be reported for the interaction models. The tabular summary will also include results from an analysis of time to death or mechanical ventilation controlling for age and duration of symptoms as continuous covariates and baseline d-dimer and CRP values as continuous covariates.

The primary analysis will also be repeated using the other subgroups defined in Section [6.4](#) in place of actual baseline Clinical Status. Each subgroup will be considered separately, and the tabular and graphical summaries described in the previous section will be replicated for each subgroup. A forest plot ([Figure 8](#), [Figure 9](#), [Figure 10](#), [Figure 11](#)) will be generated to display the overall treatment hazard ratio estimate and CI from each of the within-subgroup analyses ([Table 17](#)).

As noted in Section [6.4](#), analyses that take into account concomitant medication will be performed ([Table 18](#) and [Table 19](#)).

In addition, a forest plot will be generated for the “leave one out” sensitivity analyses described in Section [6.7](#) ([Figure 12](#)); estimated proportions and CIs will be provided for each subgroup that leaves a single site out.

Two corroborative summaries will also be generated. A summary of the number and percentage of subjects in each treatment group who:

- recovered (and are alive),
- did not recover and did not require mechanical ventilation or ECMO (and are alive),
- did not recover and required mechanical ventilation or ECMO (and are alive), and
- dead by Day 29.

The summary will also include the numbers and percentages, grouping deaths and ventilation required together ([Table 20](#)). The summaries will also be provided by the duration of symptoms categorizations specified in Section [6.4](#).

Other censoring techniques and additional analyses of the primary outcome may be performed.

8.2.2. Additional Analyses of Clinical Status Ordinal Scale at Day 15

Analysis of the key secondary outcome measure, the distribution of the Clinical Status 8-point ordinal score at Study Visit Day 15 will be repeated in the subgroups defined in Section [6.4](#) ([Table 21](#)).

In addition to the subgroup analyses, the main analysis will be repeated including a treatment * baseline ordinal score interaction term, where the interaction term p-value will be reported for the interaction model ([Table 21](#)).

8.2.3. Additional Analyses of Failure to Progress to Clinical Status 6, 7, or 8

Additional analyses as described for the mechanical ventilation free survival (Section [8.2.1](#)) will be performed ([Table 24](#), [Table 25](#), [Table 26](#), and [Table 27](#)).

